5. RANDOMIZATION, ALLOCATION CONCEALMENT AND BLINDING

5.1. Randomization

Patients will be stratified by geographic region (US, outside the US), and by completion of a COVID-19 vaccination regimen or participation in a COVID-19 vaccine clinical trial (yes, no). The randomization sequence will be developed by a qualified FHI 360 Randomization Statistician (RS) who is not otherwise involved in the study using a validated program written in SAS®.

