9.2. Analysis of Secondary Outcome Measures

Secondary efficacy analyses will be performed using the FAS unless otherwise specified. Individual data listings of NIAID ordinal scale results, symptom score questions and overall symptom score will be provided for each available day of record along with treatment arm, randomization strata, age, race, and sex for each patient.

In the event of missing NIAID ordinal assessments, any available hospitalization records, supplemental oxygen use information, or death information, as well as patient reported outcomes, will be used to impute the NIAID ordinal score if possible, particularly for ordinal scores by Days 7, 14, 28 and 60. This imputation will be conducted in a blinded fashion by the medical monitor and results will be provided to the data management/statistical team. If there is a missing assessment that is unable to be imputed using the data described above, but the missing assessment occurs between two non-missing assessments, then the higher non-missing score will be imputed for the missing score. Imputed scores will be used in the analyses below (unless specified otherwise, i.e., for sensitivity analyses) and any missing scores that are unable to be imputed will be ignored. If less than 5% of expected NIAID ordinal assessments are missing and unable to be imputed, then any impact on analysis will be considered negligible and no further action will be taken. If 5% or more are missing and unable to be imputed, then the study team will consider imputing an appropriate “high score” that is reasonable based on other responses. This “high score” will be chosen and documented prior to unblinding.

9.2.1. Proportion of patients with any progression of disease as determined by a ≥ 2 -point increase in the NIAID ordinal scale up to Day 28 and Day 60

A secondary endpoint is the proportion of patients with progression of disease as determined by a ≥ 2 -point increase in the NIAID ordinal scale up to Days 28 and 60 (e.g., a change from 2 to 4, or a change from 2 to 5). The analysis will be performed for each timepoint using a logistic regression model with a Firth penalized likelihood (Firth, 1993) at the two-sided 0.05 significance level. The model will include treatment as the independent variable. Event rates within strata will be evaluated to determine whether it is appropriate to conduct a sensitivity analysis which includes stratification by the randomization stratification factors for geographic

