region (US vs outside US) and completion of a COVID-19 vaccination regimen or participation in a COVID-19 vaccine clinical trial (yes, no).

The primary estimand of treatment effect will be the risk difference between treatment arms, corresponding 95% confidence interval (CI), and p-value based on a Wald test. The confidence interval for the risk difference will be obtained using the delta method. Additionally, the odds ratio, corresponding 95% CI, and p-value will be generated.

The proportion of patients with any progression of disease as defined above by Days 7, 14, 28 and 60 will be tabulated. A Chi-square or Fisher's exact test will compare treatment arms at each timepoint of interest.

A sensitivity analysis will be conducted mirroring analysis methods described above but excluding any imputed scores. A repeated measures modelling approach may also be considered to utilize the available longitudinal data.

9.2.2. Time to progression of disease as determined by a \geq 2-point increase in the NIAID ordinal scale up to Day 28 and Day 60

Time to progression of disease will also be assessed. Time to progression is defined as time from randomization to first occurrence of a \geq 2-point increase in the NIAID ordinal scale up to Day 60. Patients who do not have a \geq 2-point increase in the NIAID ordinal scale by Day 60 will be censored at the date of their last non-missing NIAID assessment up to Day 60. Kaplan-Meier methods will be used for the first time to event analysis. A log rank test stratified by the 2 randomization stratification factors, as appropriate, will be used to compare the 2 treatment arms. Estimates for probability of progression at Days 7, 14, 28, and 60 days, as well as median time to progression, will be derived from Kaplan Meier analysis.

Cox's proportional hazards model stratified by the 2 randomization stratification factors, as appropriate, will also be used to derive a hazard ratio and 95% CI assessing treatment effect, along with comparisons of the timepoint estimates at Days 28 and 60, if warranted. The proportional hazards assumption necessary for both the log rank test and Cox's proportional hazards model will be assessed. Any alternative methods used will be described in the CSR.

Two sensitivity analyses will be conducted mirroring analysis methods described above:

1. Excluding any imputed scores.
2. Imputing missing data when there is no collected data, as follows:

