12. EXPLORATORY ANALYSES

12.1. Subgroup Analysis and Adjustment for Covariates

All subgroup analyses and covariate adjustments will be treated as exploratory since the study was not powered for such analyses. These analyses will be conducted using the FAS, unless otherwise specified. The following baseline characteristics will be considered for subgroup analyses and covariate adjustment in statistical models. Additional baseline factors may be considered for these analyses and a decision on which factors to include will be made while the study team remains blinded.

- Age group (18-59, \geq 60 years). For regulatory purposes, an additional analysis may be performed using age groups defined as 18-64, and \geq 65 years. If there are enough patients \geq 75 years or \geq 85 years, these categories may be included.
- Number of pre-existing medical conditions which put patients at higher risk of progression to severe COVID-19 (0-1, 2 or more), based on Inclusion Criterion 3b. Note: age will be considered separately as denoted above. If there are enough patients for any specific pre-existing condition in Inclusion Criterion 3b, a subgroup analysis may be performed for this.
- Duration of any COVID-19 symptoms (0-2, 3-5 days)
- Baseline NIAID ordinal score (1, 2)
- Gender (male, female)
- Race (White, Black or African American, Asian, all others)
- Ethnicity (Hispanic or Latino, Not Hispanic or Latino)
- Body mass index ($<18.5 \text{ kg/m}^2$, $18.5 \text{ to } <25 \text{ kg/m}^2$, $\geq 25 \text{ to } <30 \text{ kg/m}^2$, $\geq 30 \text{ kg/m}^2$)
- Baseline SARS-CoV-2 variant (groupings to be determined based on prevalence)
- Use of approved/authorized COVID-19 therapies prior to randomization (if there are sufficient number of patients)

In addition to the above baseline factors, the following 2 randomization stratification factors will be used for subgroup analyses and included in all covariate adjustment models if there are sufficient patients in each of the strata.

- Region (US, outside US)
- Completion of a COVID-19 vaccination regimen or participation in a COVID-19 vaccine clinical trial (yes, no).

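### The NIAID progression endpoint needs a score of 3 from entry at 1 but 4 from entry at 2, and its planned models leave out entry score

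*SAP*

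**What the plan says.** Section 9.2.1 analyses "progression of disease as determined by a ≥ 2 -point increase in the NIAID ordinal scale up to Days 28 and 60". Its two examples both start from a score of 2: "e.g., a change from 2 to 4, or a change from 2 to 5". Section 12.1 nevertheless lists "Baseline NIAID ordinal score (1, 2") among the baseline factors, so entry at either score is expected.

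The planned analyses use these terms:

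- **9.2.1, Firth logistic model:** "The model will include treatment as the independent variable". A sensitivity analysis may stratify by "region (US vs outside US) and completion of a COVID-19 vaccination regimen or participation in a COVID-19 vaccine clinical trial (yes, no"), if event rates within strata make that appropriate.
- **9.2.2, log-rank test:** "A log rank test stratified by the 2 randomization stratification factors, as appropriate, will be used to compare the 2 treatment arms".
- **9.2.2, Cox model:** "Cox's proportional hazards model stratified by the 2 randomization stratification factors, as appropriate, will also be used to derive a hazard ratio".
- **5.1, randomisation:** "Patients will be stratified by geographic region (US, outside the US), and by completion of a COVID-19 vaccination regimen" or vaccine-trial participation. Baseline NIAID score is not a factor.
- **12.1, exploratory adjustment:** baseline NIAID score is a candidate. It enters only after a screen at p < 0.1 and then stepwise selection, and endpoints other than the primary are adjusted only where this is judged warranted.

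**The concern.** The endpoint is a change from baseline, so entry score sets how far a patient must deteriorate in absolute terms to count as an event. Two patients with the same worst score of 3 are classified differently. The pooled proportion therefore combines two thresholds, and the mix is not shown: section 8.3 does not name NIAID score among the baseline disease characteristics, and no table of progression by entry score is specified.

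The main analyses of secondary endpoints 1a and 1b also omit the baseline value of the scale that defines them. Section 9.2.3 treats the symptom score differently, with its own baseline as a fixed effect. What is at stake is the meaning of the pooled estimates and a little precision on two secondary endpoints. The primary endpoint is not affected.

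**Working it through.** **The plan's own figure.** The SAP gives no event rate or power for NIAID progression. Its only design figure is for the primary endpoint: at least 80% power with about 500 patients randomised 1:1, 2.4% vs 8.0%, two-sided 0.05. With 250 per arm and a normal approximation using the pooled variance under the null, power is 80.7%, so that figure is reproduced. It does not carry over to the NIAID endpoints.

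**Threshold.** Score needed = baseline + 2.

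| Entry score | Score needed | Worst score exactly 3 | Worst score 4 or more |
|---|---|---|---|
| 1 | 3 | event | event |
| 2 | 4 | no event | event |

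**Dependence on the mix.** These inputs are assumed. The placebo probability of a worst score of exactly 3 is q3 = 3%, and of 4 or more is q4 = 5%, the same from either entry score. A share w enters at 1. The risk ratio on scores of 4 or more is 0.30, and on score 3 it is r.

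- Placebo risk = q4 + w × q3.
- Active risk = 0.30 × q4 + w × r × q3.
- At w = 0: 5.0% vs 1.5%, risk difference −3.5 points, risk ratio 0.30.
- At w = 50% and r = 0.30: 6.5% vs 1.95%, risk difference −4.55 points, risk ratio 0.30.
- At w = 50% and r = 1: 6.5% vs 3.0%, risk difference −3.5 points, risk ratio 0.46.

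If treatment acts equally on score 3, the risk difference moves with the mix. If it does not act on score 3, the ratio moves, and with rare events the hazard ratio behaves much like the risk ratio. In between, both move. Under r = 1 and w = 50%, the ratio becomes 0.40 with q3 = 2% and q4 = 6%, and 0.62 with q3 = 5% and q4 = 3%.

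**Chance imbalance and precision.** Assume 250 per arm, half entering at each score, and progression rates by entry score of 3% vs 8% (pooled 5.5%) or 2% vs 10% (pooled 6%).

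- SD of the between-arm difference in entry-score share = √(2 × 0.25 / 250) = 4.5 points, so 2 SD is about 9 points.
- Shift in the risk difference at 2 SD = 0.089 × 0.05 = 0.4 points, or 0.089 × 0.08 = 0.7 points.
- Standard error of the risk difference = √(2 × 0.055 × 0.945 / 250) = 2.0 points, or √(2 × 0.06 × 0.94 / 250) = 2.1 points. The shift is therefore about 0.2 to 0.35 standard errors.
- Share of variance explained by entry score = 0.25 × d² / (p(1 − p)): 0.25 × 0.05² / (0.055 × 0.945) = 1.2%, and 0.25 × 0.08² / (0.06 × 0.94) = 2.8%.
- Expected events = 500 × 0.055 = 27.5, or 500 × 0.06 = 30.

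**Strata.** Region (2) × vaccination (2) × entry score (2) = 8 cells for about 30 events. Vaccinated patients are capped at about 100, and section 4.1 expects no primary events among them.

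**The case against.** The strongest reply is that nothing here is an error. Any endpoint defined by within-patient change has this property, the rule is unambiguous from any entry score, and the examples are only illustrations. Section 12.1 already names baseline NIAID score for subgroup and adjusted analyses, 9.2.1 permits a repeated-measures model, and 12.2 permits further adjusted analyses. Outcomes that do not depend on entry score are also planned, namely the primary endpoint and supplemental oxygen. Most of this stands. What it leaves open is that all those analyses of the NIAID endpoints are optional or data-selected, while the main estimates remain unadjusted and are not broken down by entry score.

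A reader might also infer more than the document supports:

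- **Bias.** The rule is identical in both randomised arms, so there is no systematic bias. Randomisation is not stratified on entry score but balances it in expectation, and the unadjusted interval already allows for chance imbalance.
- **Entry score must be prognostic because it sets the threshold.** Entry at 2 has the higher threshold but is also the worse starting state, and the two can offset. The direction and size are not in the SAP.
- **A large loss of power.** With half entering at 1 and no treatment effect on score 3, power falls from 60% to 45% in the 3%/5% scenario, relative to a fixed threshold of 4. With equal effect on score 3 it rises instead, to 72%. This is a matter of what the endpoint counts, and adding a covariate would not change it.
- **The plan ignores entry score.** That is true of the 9.2.1 and 9.2.2 models and not of the whole plan.

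**Conclusion.** The point holds as one of interpretation and modest efficiency, on two secondary endpoints. The event threshold differs by entry score, the pooled risk difference and hazard ratio depend on a mix that no specified table reports, and a baseline variable probably related to the event is left out of the main models. It does not show bias or an internal contradiction.

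The expected gain from adjustment is about 1 to 3% of variance under the assumed rates and 50/50 split. A 2-SD chance imbalance would move the risk difference by 0.4 to 0.7 points against a standard error of about 2. The SAP does not define the scale levels or state the share entering at each score, and entry at 1 and 2 is inferred from the categories in 12.1. If nearly all patients enter at one score, the effect is negligible. The change is worth making because it is cheap and matches the approach in 9.2.3.

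**What to change.** Before unblinding, amend the SAP as follows:

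- **9.2.1:** add baseline NIAID score (1 vs 2) to the Firth model alongside treatment. Obtain the risk difference by standardising over the observed entry scores, with a delta-method interval.
- **9.2.2:** add baseline NIAID score to the Cox model as a covariate and not as a further stratum, because 8 strata would be too sparse. Leave the log-rank strata unchanged.
- **Reporting:** tabulate progression by Day 28 and Day 60 by entry score and arm.
- **Optional:** add one supportive analysis in which all patients must reach the same absolute score, for example 4 or more. This is the part that addresses the mixed threshold directly; adjustment does not.

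The cost is SAP wording, one model term and one table. The score is already needed to derive the endpoint, so no extra patients or visits are required. The downside is one more parameter with perhaps 30 events, and an odds ratio and hazard ratio that become conditional on entry score. The standardised risk difference remains marginal.

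### The NIAID progression sensitivity analyses that exclude all imputed scores also discard progressions documented only in death, hospitalization or oxygen records

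*SAP*

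**What the plan says.** Section 9.2 sets out how missing NIAID assessments are handled, in this order.

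- **From records.** The SAP says that "hospitalization records, supplemental oxygen use information, or death information, as well as patient reported outcomes, will be used to impute the NIAID ordinal score". The medical monitor does this blinded.
- **From neighbouring assessments.** If no such data exist and the gap lies between two assessments, "then the higher non-missing score will be imputed for the missing score".
- **Not imputable.** Otherwise "any missing scores that are unable to be imputed will be ignored". If 5% or more of expected assessments remain missing, a high score chosen before unblinding may be considered.

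Section 9.2 adds that imputed scores feed the analyses unless a sensitivity analysis specifies otherwise.

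Section 9.2.1 (proportion with progression) has one such analysis: "A sensitivity analysis will be conducted mirroring analysis methods described above but excluding any imputed scores". Section 9.2.2 (time to progression) lists the same exclusion as item 1. Neither makes an exception by source of the score. In 9.2.2, patients without a 2-point increase by Day 60 "will be censored at the date of their last non-missing NIAID assessment up to Day 60". Item 2 of that section is headed "Imputing missing data when there is no collected data, as follows" and carries back the score recorded directly after a gap.

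**The concern.** A score assigned because the eCRF records a death or an admission on oxygen is a derivation from collected facts. A higher-neighbour fill or a chosen high score is an assumption about a day with no data. Calling both imputed, and then excluding everything imputed, removes the well-sourced scores together with the weak ones.

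The deletion depends on the outcome. The scores at risk are those assigned because something serious was recorded. Death is not a separate event in the definition of progression, so it counts only through the score. If the death-derived score is dropped and no observed score shows the rise, the death no longer appears as a progression. In 9.2.2 the patient is censored at an assessment that precedes a known bad outcome, which violates independent censoring.

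At stake is the interpretation. If this analysis disagreed with the main result, it would be read as fragility to imputation, when the cause could be documented events that were removed.

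**Working it through.** **1. What the exclusion removes in 9.2.1, by type of score**

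| Type of score | Basis | Can it alone make a patient a progressor? |
|---|---|---|
| Derived from death, hospitalization or oxygen records | Collected data | Yes |
| Inferred from patient-reported outcomes only | Collected data, more judgement | Yes |
| Higher neighbour | Copy of another score in the same patient | Almost never |
| High score | Chosen value, used only if 5% or more are missing | Yes, if used |

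The third row follows from the rule. The filled value equals a neighbouring score, so if the fill is 2 points above baseline, that neighbour is too. The fill can change the Day 28 status only when the higher neighbour falls after Day 28. In 9.2.2 it can move an event date earlier. So in 9.2.1 the exclusion hardly tests the neighbour rule; it acts mainly on the record-derived scores.

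**2. Who is affected**

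- A patient with an observed score at least 2 points above baseline remains a progressor. If that score came later than the record-derived one, the event is delayed, not lost.
- A patient whose rise is shown only by records loses the event. In 9.2.1 the remaining scores show no progression. If no post-baseline score remains, the SAP does not say whether the patient counts as a non-progressor or drops out. In 9.2.2 the patient is censored at the last observed assessment.
- Item 2 of 9.2.2 does not repair item 1. It is a separate run for gaps with no collected data and needs a later score, which a patient who has died does not have.

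**3. Comparison within the SAP**

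The symptom-score sensitivity analysis in Section 9.2.3 goes the other way. It assigns the worst answer after death and during a hospitalization or ER visit, and exempts questionnaires missed after those events from its 20% exclusion rule.

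**4. Illustration of size**

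The SAP gives no NIAID progression rate and no share of progressions known only from records. The only planning figures are in Section 4.1, for the primary endpoint: 2.4% vs 8.0%, about 250 per arm, two-sided 0.05, at least 80% power. They reproduce with the pooled normal formula:

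z = (0.056·√250 − 1.96·√(2·0.052·0.948)) / √(0.08·0.92 + 0.024·0.976) = (0.8854 − 0.6154)/0.3115 = 0.867, so power = 0.807.

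These rates are borrowed here as a stand-in for progression: 0.024·250 = 6 events on sargramostim and 0.080·250 = 20 on placebo. For a single two-arm comparison, the Firth estimate of each rate is (events + 0.5)/(n + 1). Patients who lose the event are counted as non-progressors unless stated.

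- **All kept, 6 vs 20:** (6.5 − 20.5)/251 = −5.6 points.
- **Half lost in each arm, 3 vs 10:** (3.5 − 10.5)/251 = −2.8 points.
- **The same loss, but affected patients leave the denominator (crude):** 3/247 − 10/240 = 1.2% − 4.2% = −3.0 points.
- **Half lost on placebo, a quarter on sargramostim (crude expected counts):** (4.5 − 10)/250 = −2.2 points.
- **4 lost on sargramostim, 2 on placebo, leaving 2 vs 18:** (2.5 − 18.5)/251 = −6.4 points.

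With equal shares lost, the difference shrinks in proportion. With unequal shares it can shrink more or grow.

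**The case against.** The strongest reply has four parts.

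**Reach.** Only sensitivity analyses of two secondary endpoints are affected. The main NIAID analyses keep the record-derived scores. The primary endpoint takes ER visits, hospitalizations and deaths by Day 28 straight from the eCRFs (Section 9.1), and these are also listed by patient. This stands, and it limits the weight of the point.

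**Mechanism.** The SAP does not say who completes the scale, on which days, or whether scoring continues in hospital or records death. If sites score the scale throughout admission and at death, few patients are affected. This stands. A reader might infer that the sickest patients as a class become non-progressors or are censored. The SAP does not support that: only patients with no observed 2-point rise are involved, and their number is not given.

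**Direction and size.** A reader might infer that the exclusion always pulls the difference towards zero, or that it would cost a known amount of power. Neither is supported. The case of 2 vs 18 events widens the difference. With half the events lost, the chance of p<0.05 is 0.42 by exact enumeration of the Firth Wald test on the log-odds scale and 0.50 by the normal approximation. Both rest on borrowed rates, which include ER visits that need not be 2-point rises, and on an assumed share. The SAP states no power for this endpoint.

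**Purpose.** An analysis of observed assessments only has a use: it shows how far the result depends on the medical monitor's mapping of records to scores. This is fair, and is a reason to keep that run as a supplement. It does not justify a sole exclusion rule that treats a recorded death like a guess.

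Sections 4.5 and 5.3 allow further missing-data decisions at blinded review. That gives a route for correction but does not change what the text now prescribes.

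**Conclusion.** The point holds on the wording. Sections 9.2.1 and 9.2.2 item 1, read with Section 9.2, remove progressions documented only in death, hospitalization or oxygen records, and in 9.2.2 they replace them with informative censoring. The conclusion that events are lost rests on the text alone and needs no assumed rates.

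The size cannot be determined from the SAP. It depends on how many 2-point rises are never shown by an observed assessment, and the direction depends on how that share divides between the arms. The move from -5.6 to -2.8 points assumes primary-endpoint planning rates, half of the events lost in each arm, and affected patients counted as non-progressors. It is an illustration and not an estimate. The trial's main conclusions are not at risk; the reading of a robustness check is. It should be corrected before unblinding, because a later redefinition would look driven by results.

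**What to change.** - In 9.2.1 and in 9.2.2 item 1, limit the exclusion to scores imputed without source records: higher-neighbour fills, any high score, and scores inferred from patient-reported outcomes only.
- State in both places that scores derived from Death, Hospitalization or supplemental-oxygen eCRF records are retained as observed.
- Carry a flag for the source of each NIAID score in the analysis dataset, set at the blinded review already planned.
- Optionally keep the run on observed assessments only as a labelled supplement, so that dependence on the medical monitor's mapping stays visible. For that run, say whether a patient with no remaining post-baseline score counts as a non-progressor or leaves the denominator.

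**Cost.** One sentence in two places, one derivation flag and, if the supplement is kept, one extra run. No new data are needed. The downside is that the revised sensitivity analysis still relies on the monitor's mapping of records to scores.

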4. GENERAL ANALYTIC CONSIDERATIONS

4.1. Study Size and Power

A total of approximately 500 patients will be randomized using a 1:1 assignment ratio. The sample size is selected to achieve at least 80% power to detect a difference at the 0.05 level of significance (2-sided) in the proportion of patients who experience any emergency room visit or hospitalization, or death over 28 days.

This sample size is based on an assumed 3% event rate for the sargramostim arm and a 10% rate for the placebo arm (risk ratio of 0.30) in unvaccinated patients (similar to that observed for bamlanivimab BLAZE-1 study [Chen, 2021; Gottlieb, 2021; US FDA, 2021]). As discussed in protocol Section 4.6, the rate of any emergency room visits or hospitalization, or death over 28 days is expected to be very low, or near zero for vaccinated patients.

It is also assumed that the proportion of vaccinated patients will be approximately 20-25% of the study population, with enrollment of patients who have completed a COVID-19 vaccination regimen or participated in a COVID-19 vaccine clinical trial capped at approximately 100 patients; no events are expected to occur in these patients for either treatment arm. Therefore, the overall event rate (for unvaccinated and vaccinated patients combined) for the primary endpoint is expected to be 2.4% for sargramostim and 8.0% for placebo (risk ratio of 0.30) and maintains at least 80% power.

Note that completion of a COVID-19 vaccination regimen or participation in a COVID-19 vaccine clinical trial (yes, no) is one of the randomization stratification factors (protocol Section 6.2).

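### The hazard ratio for NIAID progression (SAP 9.2.2) comes from an ordinary Cox model, although 9.2.1 uses a Firth penalty for the same events; with an event-free arm it has no finite estimate and no usable Wald interval.

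*SAP*

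**What the plan says.** Secondary endpoints 1a and 1b rest on the same event, a rise of at least 2 points on the NIAID ordinal scale.

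- **SAP 9.2.1 (proportion, Days 28 and 60):** "The analysis will be performed for each timepoint using a logistic regression model with a Firth penalized likelihood". The treatment effect is a risk difference with a Wald p-value and a delta-method interval. An odds ratio with 95% CI is added.
- **SAP 9.2.2 (time to first event, to Day 60):** Kaplan-Meier estimates and a stratified log-rank test come first. A Cox model, with region and vaccination status as strata where suitable, "will also be used to derive a hazard ratio and 95% CI assessing treatment effect". No penalty, no interval type and no rule for an event-free arm is given. The one model check named is proportional hazards.
- **Fallbacks:** Section 4.6 allows unnamed alternative methods when assumptions or distributions fail. Section 9.2.2 adds only that alternatives will be described in the CSR.
- **Event rates:** Section 4.1 gives rates for the primary endpoint only; the overall rate "is expected to be 2.4% for sargramostim and 8.0% for placebo (risk ratio of 0.30) and maintains at least 80% power". No rate is given for NIAID progression.

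**The concern.** The plan guards against sparse data when it analyses progression as a proportion, and drops that guard when it analyses the time to the same progressions. It gives no reason for the difference.

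In a Cox model with treatment as the only covariate, an arm without events makes the partial likelihood monotone. The log hazard ratio runs to minus or plus infinity, and the standard error on which a Wald interval depends becomes meaningless. Short of that, a small event count biases the estimate away from 1.

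The failure is most likely when the drug works well. A replacement method might then have to be chosen once the split of events by arm is known. At stake is the hazard ratio reported for secondary endpoint 1b.

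**Working it through.** **Inputs.** From SAP 4.1: "A total of approximately 500 patients will be randomized using a 1:1 assignment ratio", so 250 per arm; an "assumed 3% event rate for the sargramostim arm and a 10% rate for the placebo arm" among unvaccinated patients; and, for vaccinated patients, "no events are expected to occur in these patients for either treatment arm". With 20% vaccinated, 0.80 × 3% = 2.4% and 0.80 × 10% = 8.0%.

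**The plan's own figure.** Pooled-variance test of two proportions, n = 250 per arm, mean rate 0.052:

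- Numerator: 0.056 × √250 − 1.96 × √(2 × 0.052 × 0.948) = 0.885 − 0.615 = 0.270
- Denominator: √(0.024 × 0.976 + 0.080 × 0.920) = 0.311
- Power = Φ(0.270 / 0.311) = Φ(0.867) = 80.7%

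This reproduces the stated power of at least 80%. It concerns the primary endpoint only.

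**Step 1: what the ordinary Cox model does with an event-free arm.** Constructed data had 250 vs 250 patients, no sargramostim events, and 5, 10 or 20 placebo events on distinct days. All other patients were censored at Day 60, and no strata were used. With 5 events the log partial likelihood is −31.05 at log HR 0, −27.60 at −5 and −27.567 at −20. It keeps rising and has no maximum. In all three data sets the fit failed to converge, with HR about 0 and a Wald interval of 0 to infinity.

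Other quantities from the same data:

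| Events (sargramostim vs placebo) | Log-rank chi-square | Ordinary profile-likelihood 95% limits | Firth HR (penalised profile 95% CI) |
|---|---|---|---|
| 0 vs 5 | 5.0 | 0 to 0.46 | 0.090 (0.0007 to 0.79) |
| 0 vs 10 | 10.2 | 0 to 0.21 | 0.047 (0.0004 to 0.36) |
| 0 vs 20 | 20.8 | 0 to 0.097 | 0.023 (0.0002 to 0.17) |

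The Firth version maximises log L(β) + ½ log I(β). Hand checks for 0 vs 5: with nearly equal risk sets the profile upper limit solves 2 × 5 × log(1 + HR) = 3.84, so HR = e^0.384 − 1 = 0.47. The Firth estimate should be near 0.5 / 5.5 = 0.091.

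**Step 2: how likely is an event-free arm?** P(no event in an arm) = (1 − p)^250, combined over the two arms as a + b − ab. The progression rate is an assumption, shown as a fraction of the primary rates with the risk ratio held at 0.30.

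| Assumed fraction | Rates | Expected events | No sargramostim event | Either arm without events |
|---|---|---|---|---|
| 100% | 2.4% vs 8.0% | 6 vs 20 | 0.2% | 0.2% |
| 75% | 1.8% vs 6.0% | 4.5 vs 15 | 1.1% | 1.1% |
| 50% | 1.2% vs 4.0% | 3 vs 10 | 4.9% | 4.9% |
| 25% | 0.6% vs 2.0% | 1.5 vs 5 | 22.2% | 22.7% |

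**Step 3: bias when the estimate is finite.** Under constant hazards, the true log HR for 2.4% vs 8.0% is log[ln(0.976) / ln(0.920)] = log(0.02429 / 0.08338) = −1.23. (The log risk ratio, log 0.30 = −1.20, is a different quantity.) In simulated trials with 250 per arm, ordinary Cox fits average about −1.29 when finite, and Firth fits about −1.23. The standard deviation of the ordinary estimate is about 0.51, so the bias of 0.06 is about 12% of one standard deviation. Averages at lower rates are not compared, because restricting to finite fits discards the trials with no sargramostim event.

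**The case against.** An ordinary stratified Cox model beside a log-rank test is conventional. The log-rank test is the stated comparison, and the hazard ratio is an additional summary of one secondary endpoint in a Phase 2b trial. Several stronger readings are tempting, and the SAP does not support them.

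- **That no interval could be computed.** Only the Wald interval is lost. The SAP does not fix the interval type in 9.2.2, and a profile-likelihood interval keeps a finite upper limit.
- **That only a p-value would remain.** Kaplan-Meier probabilities at Days 7, 14, 28 and 60 survive, as do the risk difference and odds ratio of 9.2.1. For 0 vs 5 events, the Firth odds ratio is (0.5 / 250.5) / (5.5 / 245.5) = 0.089, almost the same as the Firth hazard ratio of 0.090.
- **That failure is likely.** At the only rates the SAP states, the chance is about 0.2%. Progression could be rarer than the primary endpoint, which counts any ER visit. But it is also counted to Day 60 rather than Day 28, and a gap between two NIAID scores may be filled with the higher one. Neither direction is quantified.
- **That event-free vaccinated strata break the model.** A stratum without events only contributes no information to a stratified Cox model.
- **That the method must be changed after unblinding.** Blinded review (Section 5.3) could see a low pooled count and prompt a penalised model beforehand.

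These points limit the harm but do not remove the gap. Section 4.6 names no method. An event-free arm cannot be recognised from pooled data, and it is not a failure of proportional hazards, the only check that 9.2.2 names.

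**Conclusion.** The point holds as a cheap improvement. The plan uses a Firth penalty for progression as a proportion and none for time to the same progression. An event-free arm would leave the hazard ratio without a finite estimate and its Wald interval undefined. At the primary endpoint rates, the ordinary estimate is also slightly biased away from 1.

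The zero-event probabilities (about 0.2%, 5% and 23%) assume 250 evaluable patients per arm, a risk ratio of 0.30, and progression at the full, half or quarter primary rate. The lower two rates are assumptions with no figure in the SAP behind them. The bias figure also assumes constant hazards and an unstratified fit. Nothing here touches the primary endpoint, the log-rank test or the analyses in 9.2.1.

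**What to change.** In 9.2.2, specify that the stratified Cox model is fitted with Firth's penalised partial likelihood, and that the hazard ratio is reported with a profile-penalised-likelihood 95% CI. Leave the log-rank test and Kaplan-Meier estimates as they are, and make the change before unblinding.

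The penalty follows the approach of 9.2.1. The profile interval does not: 9.2.1 uses a Wald test and a delta-method interval, so this interval would be new to the SAP and should be named explicitly.

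The cost is one sentence and one program option. The downside is slight shrinkage of the hazard ratio toward 1 when events are very few.
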